2.2 Risks

Intervention-specific Risks

The main risk to participants in the current study consists of a change in the level of effectiveness and side effects from treatment as a result of the study intervention. Specifically, the “intervention” group may experience a different rate of response, or notice side effects to a different degree than the “treatment as usual” group.

Although non-specific effects in general are believed to be responsible for a significant portion of the treatment’s effects, as the current study only targets a small subcategory of non-specific factors, the magnitude of increased risk will be limited. Furthermore, the study is designed to create a difference between groups mainly by potentially improving the outcomes of the “intervention” group.

The “intervention” group may also experience more dysgeusia which is one of the mild and temporary side effects of esketamine, as a result of intentionally highlighting it in the presentation.

Additionally, the “intervention” group may experience some distress during the “post-treatment” session, particularly if they need to review and discuss distressing or uncomfortable experiences from the treatment.

Psychiatric Assessment and Symptom Rating

Discussing symptoms or past experiences can sometimes be stressful. All included evaluations are non-invasive and have been used without difficulty or adverse events in previous studies and clinical practice.

In order to minimize risks associated with the psychiatric ratings and ensure the accuracy of reporting, these measures will be administered by trained research staff. Participants will be informed that they do not need to answer any question on the rating scales or questionnaires that make them feel uncomfortable. Participants will also be informed they can take a break if they become tired from any of the questions or ratings.

Confidentiality

Loss of confidentiality is another potential hazard of any research protocol. The investigators follow a system of specific precautions to ensure the confidentiality of data in this protocol.

Private identifiable information will be collected (name, date of birth, age, telephone number, address, medical and psychiatric history, diagnoses, laboratory tests, and psychiatric rating scores) but will be kept confidential and will not be divulged in any publication emanating from this work. Please see section 8.1, for the protections in place to mitigate confidentiality risks.

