The intervention consists of a short presentation provided to the participants within 72 hours prior to the first treatment of the acute course (see study course below). Both groups will receive the information considered necessary for informed consent for esketamine treatment as part of usual clinical care. The presentation will be in addition to this process. The presentation will be factual, however it will emphasize the effectiveness of the treatment, and provide notable encouragement and reassurance. The actual treatments will be provided as usual with no change or alteration in dosing, course or other aspects of the treatment.

The intervention group will additionally receive a follow up session within 24 hours after the first treatment to provide encouragement and reassurance. There are two different versions for the follow up session, with each participant receiving one of the versions depending on whether they have noticed any improvements since the first treatment. The contents of these sessions will remain factual, but with differing emphasis on encouragement and reassurance depending on participants’ experience with the first treatment.

Study course

Participants in the intervention group will receive the presentation within 48 hours before the first treatment of the acute course of esketamine. They will also receive the follow up session within 24 hours after the first treatment, immediately after assessments are completed.

Assessments will be done at baseline, within 24 hours after treatments 1, 2 and 8, as detailed in Table 1. Assessments will be identical for both groups, with the exceptions described below.

Assessments

Intervention group specific assessments:

Participants will provide feedback regarding the presentation using a custom form (Appendix 1) before treatment 1 and at the end of treatment visit.

Assessments received by both groups:

Participants’ expectations will be assessed by Treatment Credibility and Expectancy Scale (CEQ-6).

[figure not shown]
Symptom severity will be assessed by a blinded assessor using a Clinician Rated Outcome questionnaire (MADRS) and a Patient Rated Outcome questionnaire (QIDS-SR16).

[figure not shown]
Side effects will be assessed by a custom questionnaire (Appendix 2) based on the side effects reported on the prescription label for esketamine.

End of treatment debriefing session:

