6.3 Adverse Events Definition and Reporting

Study investigators will be able to remove patients from the trial based on their clinical discretion and specific patient outcomes. Any adverse events, including grading of severity and attribution to research will be reported.

In this study, AEs will be defined as any event associated with virtual presentation and follow-up sessions whether or not considered intervention related. This includes any physical, psychological or emotional harm, or any other unintended effects experienced by the participant. Adverse events will be considered from the time of consent and will be monitored and recorded throughout the study. AEs evaluation will be done 24 hours after the first treatment and within 72 hours after 8th treatment. Participants will be asked to report any AEs they experience, either spontaneously or during the study visits. AEs will be recorded on the appropriate CRF. Patients will be closely monitored for adverse events.

The following adverse events will be collected from the time of randomization for the study:

- Adverse events that are not listed in the current labeling for esketamine. This includes events that are similar to those on the labeling but differ from the event because of greater severity or specificity.
- Study Treatment Discontinuation Adverse Events
- Events that lead to the discontinuation of esketamine will be collected for the study. These events will be recorded on either an AE or an SAE form.

The study team will document the AEs, its severity, relationship to the intervention, and the actions taken to address it.

An adverse event (AE) or suspected adverse reaction is considered "serious" if, in the view of either the investigator or sponsor, it results in any of the following outcomes: death, a life-threatening adverse event, inpatient hospitalization or prolongation of existing hospitalization, a persistent or significant incapacity or substantial disruption of the ability to conduct normal life functions, or a congenital anomaly/birth defect.

Note: In addition to AEs as described above, a separate side effect form will be collected during the trial which will solely focus on known side effects of esketamine as per the current labeling (See appendix 2).

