7.2.1 Secondary Objective Analyses

Please see above for the analysis of secondary efficacy outcomes (MADRS and QIDS). To examine the safety and tolerability of the intervention for the duration of the study, we will use descriptive statistics to characterize the rates of these events in the intervention group.

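### Section 7.2.1 summarises safety and tolerability in the intervention group only, although unlabelled esketamine events and esketamine discontinuations are collected without limit to one arm; report them by randomised arm

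*Combined protocol and SAP*

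**What the plan says.** Section 7.2.1 refers the efficacy outcomes back to 7.2 and then, for the safety and tolerability of the intervention, says "we will use descriptive statistics to characterize the rates of these events in the intervention group". Nothing earlier in that section says which events are meant.

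On collection, Section 4 (Study Design) says "Assessments will be identical for both groups, with the exceptions described below". The only exception it lists is the presentation feedback form. Under the assessments that both groups receive it says "Side effects will be assessed by a custom questionnaire (Appendix 2) based on the side effects reported on the prescription label for esketamine". Section 6.3 says "The following adverse events will be collected from the time of randomization for the study", and its list includes "Adverse events that are not listed in the current labeling for esketamine" and "Events that lead to the discontinuation of esketamine will be collected for the study". Neither item is restricted to one arm.

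On purpose, Section 2.2 says that the main risk "consists of a change in the level of effectiveness and side effects from treatment as a result of the study intervention", and that the intervention group may "notice side effects to a different degree than the" TAU group. Hypothesis 4 (3.2) predicts a difference in the side-effect profile, and 4.2.2 lists the group difference in that profile as an exploratory outcome.

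On analysis, the mixed model in 7.2 names CEQ-6, MADRS and QIDS. Section 7.3 includes questionnaire side effects among the data to be compared between the intervention and TAU groups. It does not mention adverse events.

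**The concern.** The trial randomises a way of presenting a treatment that every participant is already scheduled to have. Events in the intervention arm are therefore a mixture: some would have occurred with esketamine alone, and some may have been brought on, averted or made more noticeable by the presentation. Only the TAU arm separates the two. If 7.2.1 is followed as written, unlabelled esketamine events and esketamine discontinuations would be gathered in both arms and summarised in one. The control data that give the rate its meaning would go unused.

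What is at stake is the safety report and an exploratory endpoint. The expectancy and depression outcomes have their own between-group model and are not touched.

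**Working it through.** This is mainly a matter of reading the sections together. A short calculation then shows what a one-arm rate leaves open.

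**Step 1. Which analysis statement covers which data?**

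| Data | Collected in | Analysis statement |
|---|---|---|
| CEQ-6, MADRS, QIDS | both arms (4; Table 1) | between-group mixed model (7.2) |
| Side-effect questionnaire | both arms (4) | between-arm comparison promised in 7.3; possibly also 7.2.1 |
| Unlabelled esketamine events; events leading to esketamine discontinuation | no limit to one arm (6.3) | 7.2.1 only: intervention group |
| Events arising from the presentation or follow-up session | intervention arm only, since TAU has neither | 7.2.1: intervention group |

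The third row is the problem. In the fourth row a one-arm summary is all that is possible. In the second, 7.3 already points to a comparison.

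**Step 2. Can a one-arm rate answer the question?** Write the intervention-arm rate as p1 and the TAU rate as p2. The effect of the presentation on an event is p1 - p2. Section 7.2.1 reports p1 and leaves p2 out, so the difference cannot be recovered.

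**Step 3. Illustration.** Inputs: 17 per arm (5.2, 7.1) and no dropout (assumed). All event counts are assumed, because the documents give no event rates. The one-arm interval is the exact (Clopper-Pearson) 95% CI. The interval for the difference is Newcombe's, built from the Wilson limits (l, u) of each arm:

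lower = (p1 - p2) - sqrt[(p1 - l1)² + (u2 - p2)²]

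upper = (p1 - p2) + sqrt[(u1 - p1)² + (p2 - l2)²]

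Suppose 2/17 in the intervention arm discontinue esketamine because of an event. The one-arm summary is 2/17 = 11.8% (1.5 to 36.4%). It is the same in each of these cases:

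| TAU count | Difference, points (95% CI) |
|---|---|
| 0/17 | 11.8 - 0 = +11.8 (-8.5 to 34.3) |
| 2/17 | 11.8 - 11.8 = 0 (-24.1 to 24.1) |
| 4/17 | 11.8 - 23.5 = -11.8 after rounding (-37.0 to 14.8) |

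The last row is (2 - 4)/17 = -2/17. The one-arm figure fits a rise, no change or a fall.

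A commoner event behaves the same way. With 8/17 in the intervention arm (47.1%; 23.0 to 72.2%), the difference is 41.2 points (11.5 to 63.7) if TAU has 1/17, and 0 (-30.3 to 30.3) if TAU has 8/17.

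The intervals are wide, as they must be with 17 per arm. That favours reporting an estimate with its interval over relying on a test.

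**The case against.** The best defence is that 7.2.1 concerns the safety of the intervention, meaning the presentation and the follow-up session. Section 6.3 opens by defining adverse events as those associated with these sessions, which TAU never receives, and it treats the side-effect form as separate. On that reading a one-arm rate is natural. Distress during the follow-up session, which 2.2 names as a risk, can occur only in the intervention arm. This part of the defence stands. It does not cover the rest of 6.3, which goes on to collect unlabelled esketamine events and esketamine discontinuations without regard to arm, nor the Glossary, whose definition of an adverse event includes esketamine treatment.

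A reader might also infer more than the documents support:

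- **That the plan drops the between-arm comparison of side effects.** It does not. Section 7.3 promises it, and 4.2.2 words the endpoint as a group difference. Because the events meant in 7.2.1 are never identified, that section is ambiguous for the questionnaire, not in proven contradiction with 7.3.
- **That the main risk in 2.2 goes unexamined.** Its effectiveness half is compared between arms by the 7.2 model on MADRS and QIDS.
- **That leaving the side-effect variable, visit and method open inflates false positives.** The two-tailed 0.05 threshold in 7.2 names CEQ-6, MADRS and QIDS, and no test is specified for side effects. An error rate would have to presume tests that the plan does not contain. The open choices are missing detail on an exploratory endpoint and do not carry this point.

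**Conclusion.** The point holds for adverse events that can occur in either arm. For these, 7.2.1 is the only analysis statement, and it leaves out the control arm although 6.3 does not limit collection to one arm. For questionnaire side effects it is at most an ambiguity, to be settled in line with 7.3, 4.2.2 and Hypothesis 4. For events that arise solely from the presentation or follow-up session, the one-arm summary is adequate.

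No stated figure in the plan is affected, and no true size can be given because the documents contain no event rates. The illustrations rest on assumed counts and full follow-up of 17 per arm. The 0/17 case for TAU is a bound, not a forecast. The logical point, that a one-arm rate cannot give a between-arm difference, does not depend on those counts.

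This is a free improvement to safety and exploratory reporting.

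**What to change.** In 7.2.1:

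1. Replace the restriction to the intervention group with: *by randomised arm (intervention and TAU) at each collection time*.
2. Add: *Events that can arise only from the presentation or follow-up session will be summarised in the intervention group alone.*
3. Add: *For Hypothesis 4 (exploratory), dysgeusia will be reported by arm as a between-arm difference with a 95% CI; the other questionnaire items will be described by arm.*

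The wording should also say which events 7.2.1 covers, so that it agrees with 6.3 and 7.3. The interval method and the lead timepoint for dysgeusia (24 hours after treatment 1, or the visit after treatment 8) are for the investigators to choose, and should be fixed before the data are seen.

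The cost is a change of wording in the protocol and SAP. No added participants, visits or forms are needed.

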7.2.2 Analysis of Subject Characteristics

Baseline characteristics will be examined using descriptive statistics, presented as means \pm SD or median (interquartile range) for continuous characteristics, and as frequencies (%) for categorical characteristics. Baseline characteristics include age, sex, ethnicity, socioeconomic status, treatment expectation (CEQ-6) and psychiatric symptoms (MADRS, QIDS).

7.2.3 Interim Analysis

NA

7.3 Data Relevance

In the study, the primary research question is whether a positive presentation highlighting the rapid onset effects and positive therapeutic outcomes of esketamine treatment, before first treatment improves expectation of improvement from treatment in patients receiving esketamine compared to the treatment-as-usual (TAU) group.

The secondary research question is whether a positive presentation results in an improved response from treatment in patients receiving esketamine for a depressive episode as measured by MADRS score within 24 hours after the first treatment.

To answer these questions, the data collected will include expectations of improvement assessed by the Treatment Credibility and Expectancy Scale (CEQ-6), symptom severity assessed by Clinician Rated Outcome questionnaire (MADRS) and Patient Rated Outcome questionnaire (QID-SR16), and side effects assessed by a custom questionnaire. These data points will be analyzed and compared between the intervention and TAU groups to determine if there is a difference in treatment response and whether the non-specific effects of the positive presentation and follow-up session have an impact.

7.4 Data Coding

In this study, data coding will be necessary for several aspects of the data collection, including participant characteristics, treatment groups, and outcome measures.

For participant characteristics, such as age, gender, and baseline symptom severity, appropriate codes can be assigned to easily categorize and analyze the data. For example, age can be coded as continuous or categorical (e.g., 18-25, 26-35, 36-45, etc.), and gender can be coded as binary (male/female).

For treatment groups, a binary code can be assigned to each participant, with 0 representing the treatment-as-usual group and 1 representing the intervention group. This will allow for comparison between the two groups.

For outcome measures, such as symptom severity and side effects, appropriate scoring systems or coding will need to be established. The symptom severity can be measured using the Clinician-Rated Outcome questionnaire (MADRS) and Patient-Rated Outcome questionnaire (QID-SR16), and these scores can be transformed into categorical or continuous variables for analysis. For the side effects, a custom questionnaire based on the side effects reported on the prescription label for esketamine will be used and side effects can be coded as present or absent.

7.5 Data Analysis Tools

R version 3.3 will be used.

7.6 Data Monitoring

Given the minimal-risk nature of the study, and as patients are simultaneously receiving treatment as part of usual clinical care, no external monitoring will be done.

7.7 Handling of Missing Data

Our primary analyses will be intent-to-treat using all available data. We will undertake sensitivity analyses to assess the impact of the missing response data on our conclusions. We will perform single-step (e.g., missing values on the response variable replaced by predicted values from linear or generalized linear models of the longitudinal data over time) or multiple imputation and compare the performance of the imputed data results compared to complete case analyses. It is important to note that the linear mixed model method we propose to use is valid under the assumption that missing data is missing at random (MAR). Since it is not possible to test the MAR assumption and since for every MNAR model there is an equally well-fitting MAR model, we believe that the only suitable approach is to perform sensitivity analyses according to different plausible scenarios for missing data and make sure the conclusions are consistent. If the results are not consistent depending on the assumptions for missing data we will report the conclusions based on each set of assumptions.

8 Data/Specimen Handling and Record Keeping

8.1 Subject Data Confidentiality

Participant confidentiality and privacy is strictly held in confidence by the participating investigators, their staff, and the sponsor(s)/funding agency. Therefore, the study protocol, documentation, data, and all other information generated will be held in strict confidence.

All research activities will be conducted in as private a setting as possible.

Representatives of the Institutional Review Board (IRB), regulatory agencies or study sponsor/funding agency may inspect all documents and records required to be maintained by the investigator for the participants in this study. The study site will permit access to such records.

The study participant's contact information will be securely stored at study site for internal use during the study. At the end of the study, all records will continue to be kept in a secure location for as long a period as dictated by the reviewing IRB, Institutional policies, regulatory, or sponsor/funding agency requirements.

Study participant research data, which is for purposes of statistical analysis and scientific reporting, will be transmitted to and stored at the office of the PI. This will not include the participant's contact or identifying information. Rather, individual participants and their research data will be identified by a unique study identification number. The study data entry and study management systems used will be secured and password protected. At the end of

the study, all study databases will be de-identified and archived on the server used by the PI's lab.

8.2 Data Quality Assurance

Data quality assurance is a crucial aspect of this study to ensure the validity and reliability of the results. A number of steps will be taken to maintain data quality, including the use of standardized and validated assessment tools (CEQ-6, MADRS, QID-SR16, and custom questionnaire), training of the blinded assessor to ensure consistent administration of the assessment tools, regular monitoring of data collection to identify and address any discrepancies, and proper storage and management of the collected data.

We will perform internal quality management of study conduct, data collection, documentation and completion.

8.3 Data or Specimen Storage/Security

The study participant's contact information will be securely stored at study site for internal use during the study. At the end of the study, all records will continue to be kept in a secure location for as long a period as dictated by the reviewing IRB, Institutional policies, regulatory, or sponsor/funding agency requirements.

Study participant research data, which is for purposes of statistical analysis and scientific reporting, will be transmitted to and stored at the office of the PI. This will not include the participant's contact or identifying information. Rather, individual participants and their research data will be identified by a unique study identification number. The study data entry and study management systems used will be secured and password protected. At the end of the study, all study databases will be de-identified and archived on the server used by the PI's lab.

Data collection is the responsibility of the clinical trial staff under the supervision of the primary investigator. The investigator is responsible for ensuring the accuracy, completeness, legibility, and timeliness of the data reported. All source documents will be completed in a neat, legible manner to ensure accurate interpretation of data.

Hardcopies of the study visit worksheets will be provided for use as source document worksheets for recording data for each participant enrolled in the study. Data recorded in the electronic case report form (eCRF) derived from source documents should be consistent with the data recorded on the source documents.

Clinical data (including adverse events (AEs), concomitant medications, and expected adverse reactions data) will be entered into an online database approved for high-risk data as per Yale's data classification). Clinical data will be entered directly from the source documents.

